4.3. Statistical Methods for Efficacy Analyses

4.3.1. Estimand Framework for the Primary Endpoint

Population: The target study population comprises children and adults with TSC-related epilepsy who also meet the inclusion and exclusion criteria as specified in the study protocol. The analysis population is the Intent-to-Treat (ITT) Population defined as all randomized participants.

Variable: The variable is the primary efficacy endpoint, the percentage change from baseline in 28-day primary endpoint seizure frequency during the double-blind phase.

Population-Level Summary: The population-level summary will be the difference of the percentage change on primary efficacy endpoint between GNX and PBO groups and its 2-sided 95% confidence interval.

Accounting for Intercurrent Events (ICEs): Intercurrent events and their handling rules are as follows:

- Discontinuations due to lack of efficacy;
- Discontinuations due to expected (per IB) adverse events.

Both ICEs will be addressed by the treatment policy strategy. The use of rescue medication is allowable at any time during the study. A patient may require rescue medication during the trial but continues with the trial post-rescue medication. The efficacy of the trial treatment will be assessed regardless of the need for rescue medication. Alternative approaches to handling ICEs will be addressed in sensitivity analyses, see Section 4.3.3.

4.3.2. Primary Efficacy Endpoint

Hypothesis testing will be performed for the primary endpoint: the percentage change in 28-day primary endpoint seizure frequency during the DB phase relative to the baseline, based on the primary endpoint seizure types. The hypothesis testing is:

$$H_0$$
: $\theta_{PBO} = \theta_{GNX}$ H_a : $\theta_{PBO} \neq \theta_{GNX}$

where θ_{GNX} is the percentage change of seizure frequency during the DB phase relative to the baseline for participants who treated with GNX and θ_{PBO} is similarly defined for participants receiving placebo.

Primary endpoint seizure types are defined as the following: focal motor seizures without impairment of consciousness or awareness, focal seizures with impairment of consciousness or awareness with motor features, focal seizures evolving to bilateral, tonic-clonic seizures, and generalized motor seizures including tonic-clonic, bilateral tonic, bilateral clonic, or atonic/drop seizures. Seizures that do not count toward the primary endpoint include: focal aware seizures without motor features (eg, focal nonmotor seizures with or without impaired awareness, absence or myoclonic seizures), infantile or epileptic spasms, and myoclonic seizures.

Post-baseline 28-day seizure frequency will be calculated as the total number of seizures in the double-blind phase divided by the number of days with seizure data in the same period, multiplied by 28. Baseline 28-day seizure frequency will be calculated as the total number of seizures in the baseline phase divided by the number of days with seizure data in the same period, multiplied by 28. The calculation for percent change from baseline in 28-day seizure frequency will be done as follows for each participant:

The baseline, post-baseline, and arithmetic and percent changes from baseline in 28-day seizure frequency will be summarized using descriptive statistics.

The difference between the treatment groups in the percent changes will be tested for statistical significance. The estimate of the median difference and corresponding 95% confidence interval based on the Hodges–Lehmann approach will be provided. Since the percent differences are anticipated to display skewness and/or outliers, the test will be performed using the Wilcoxon Rank-Sum statistic using a 2-sided significance level of 0.05.

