The Phase 2 data for GNX in TSC raised the question of a CBD interaction. In the trial of 23 treated patients, approximately half were on cannabidiol, and there was an association between higher CBD doses and increased somnolence. Given the small sample size, more definitive conclusions were not possible. As a result, patients taking CBD should be monitored closely for any sedation-related adverse events (AEs) throughout this Phase 3 protocol. Participants may have the dose of investigational product (IP) temporarily or permanently decreased at any point in the maintenance period to manage tolerability.

Any dose adjustments that are not part of the prespecified titration schedule should be discussed with the sponsor medical monitor prior to making the change. If it is not possible to contact the medical monitor prior to the dose adjustment, the medical monitor should be notified as soon as possible after making the change.

The maximum dose for all participants is 1800 mg/day. The total double-blind phase (titration and maintenance periods) should not exceed 16 weeks.

Participants who discontinue the IP should undergo a 2-week taper period. The taper period may be shortened at the discretion of the investigator as clinically indicated. Participants who discontinue the IP before the scheduled completion of the study will return to the site 2 weeks after the end of taper to complete the safety follow-up assessments.

Following completion of the double-blind phase, participants who are compliant with study conduct will have the option to enroll and be treated with GNX in a separate open-label extension study (OLE), 1042-TSC-3002. All participants entering the OLE will have their dose of study medication adjusted in a double-blind cross-titration over 4 weeks such that all are receiving GNX at study completion. Participants who do not continue in the OLE will undergo a 2- to 4-weeks double-blind down-titration and taper if discontinuing IP (See [Figure 1](#)).

Disclosure Statement:

This is a randomized, double-blind, placebo-controlled, 2-arm treatment study that is participant, caregiver, and investigator blinded.

Number of Participants:

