4.2 Scientific Rationale for Study Design

This is a Phase 3, double-blind, randomized, placebo-controlled study of adjunctive GNX treatment in children and adults with TSC-related epilepsy. Children and adults with TSC-related epilepsy are included in the study as this is one of the populations being pursued for development. The eligibility criteria allow for the selection of participants comparable to the patients seen in clinical practice.

Randomization will be used in this study to avoid bias in the assignment of participants to treatment, to prevent introducing bias into the study evaluations and statistical analyses, and to ensure participant characteristics are balanced between the GNX and placebo arms. In order to facilitate subgroup analysis, randomization will be stratified with respect to whether the participant is taking concomitant CBD or not.

All the efficacy and safety assessments included in this study are standard measures used in clinical studies in general and epilepsy trials in particular.

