3. STUDY DESIGN

3.1. Randomization

Subjects will be randomized to receive either GNX or PBO in a 1:1 ratio and randomization will be stratified based on current use of Epidiolex. Block randomization will be used with a block size specified in Rave RTSM (randomization and trial supply management) study randomization list settings document.

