3.2. Sample Size Considerations

The planned sample size for this study is 128 randomized and dosed subjects. These subjects will be allocated into 2 treatment groups, GNX vs. PBO, in a 1:1 ratio. Sixty-four subjects per group provides at least 90% power for the primary endpoint assuming an estimate of the treatment effect (the actual analysis will use a Wilcoxon rank-sum test, which has approximately the same power as the ANOVA) difference that is at least 25% and a common standard deviation of 43% or less.

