4.3.4. Key Secondary Efficacy Endpoints

Hypothesis testing will be performed for the three key secondary endpoints:

1. Percentage change from baseline in 28-day primary endpoint seizure frequency during the maintenance period.

The hypothesis testing is:

$$H_0$$
: $\theta_{PBO} = \theta_{GNX}$ H_a : $\theta_{PBO} \neq \theta_{GNX}$

where θ_{GNX} is the percentage change of seizure frequency during the maintenance period relative to the baseline for participants who treated with GNX and θ_{PBO} is similarly defined for participants receiving placebo.

Similar to the primary efficacy endpoint, the test will be performed using the Wilcoxon Rank-Sum statistic using a 2-sided significance level of 0.05.

2. Number (%) of participants considered treatment responders during the DB phase. The hypothesis testing is:

$$H_0: \gamma_{PBO} = \gamma_{GNX} \quad vs. \quad H_a: \gamma_{PBO} \neq \gamma_{GNX}$$

where γ_{GNX} is the proportion of participants who treated with GNX experiencing $\geq 50\%$ reduction from baseline in 28-day seizure frequency based on the primary seizure types and γ_{PBO} is similarly defined for participants receiving placebo.

The test comparison will be analyzed using Fisher's Exact test and the corresponding p-value will be provided. The difference in proportions along with the 95% confidence interval for the difference also will be presented. The number and percentage of subjects experiencing a reduction (improvement) of at least 50% from baseline in the 28-day seizure frequency of the primary seizure types will be summarized. In addition, a cumulative responder curve figure will be provided, in which the X-axis represents amount of improvement in increments of 5%, and the Y-axis represents the percentage of subjects improving by at least the amount on the X-axis. The treatment groups will be presented separately within the figure.

3. Number (%) of participants considered treatment responders during the maintenance phase.

This is similar to #2 above. The only difference will be replacing the DB phase by the maintenance phase.

4. CGI-I at the last scheduled visit in the DB phase.

The hypothesis testing is:

$$H_0$$
: $OR_{GNX/PBO} = 1$ vs. H_a : $OR_{GNX/PBO} \neq 1$

where $OR_{GNX/PBO}$ is the odd ratio between GNX and PBO in regard to CGI-I.

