The CGI-I is 7-point scale, and the number and percentage of subjects with each score will be summarized. The scores range from 1=very much improved and 7=very much worse. The CGI-I is completed by both parent/caregiver/LAR and clinician. The score at the last visit in the DB treatment phase will be analyzed using ordinal logistic regression. Proportional odds modelling will be carried out by including treatment group as a factor. The estimated odds ratios (GNX vs. PBO), 95% CI for the odds ratios, and the p-value testing the null hypothesis that the odds ratio is equal to 1, will be presented.

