4.3.7. Subgroup Analyses for Primary Endpoint

Summaries with descriptive statistics and frequency counts on the primary efficacy endpoint for both groups will be provided for the subgroups indicated below. Forest plots will also be created for subgroup analyses and will display treatment differences. The subgroups will be:

- Gender (female vs. male)
- Age Group (12 months to 23 months; 2 to 11 years; 12 to 17 years; 18 to 64 years; and 65 years and above)
- Country/Region (US, China, EU, ROW)

•

- Concomitantly taking everolimus (yes vs. no)
- Concomitantly taking cannabidiol (yes vs. no)
- mTOR medication (taking sirolimus, everolimus, tacrolimus vs. no)

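### Randomisation is stratified by CBD use but none of the confirmatory tests uses the stratum, and Fisher's exact test costs further power on both responder endpoints

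*SAP*

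**What the plan says.** SAP 3.1 states that "randomization will be stratified based on current use of Epidiolex", with 1:1 blocked allocation and the block size held in another document. Protocol 4.2 gives the purpose: "In order to facilitate subgroup analysis, randomization will be stratified with respect to whether the participant is taking concomitant CBD or not".

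The confirmatory tests are as follows.

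- Primary (SAP 4.3.2): "the test will be performed using the Wilcoxon Rank-Sum statistic using a 2-sided significance level of 0.05", with a Hodges-Lehmann estimate for which no stratification is mentioned. Protocol 9.3.2 names the same test.
- Key secondary 1, percent change in the maintenance period (SAP 4.3.4): the same rank-sum test.
- Key secondaries 2 and 3, responders in the double-blind phase and in maintenance: Fisher's "Exact test and the corresponding p-value will be provided".
- Key secondary 4, CGI-I: "Proportional odds modelling will be carried out by including treatment group as a factor". No other term is named.

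SAP 3.3 tests the four key secondaries in order and stops at the first non-significant result. None of the sensitivity analyses described in SAP 4.3.3 adjusts for CBD use. It returns only in SAP 4.3.7, as a descriptive subgroup of the primary endpoint. CMH and ANCOVA are in the SAP's abbreviation list, but no efficacy method in the available text uses either. No reason is given for leaving the stratum out. SAP section 7 moves the EMA primary analysis to the maintenance period without changing the method.

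**The concern.** Stratified blocked allocation balances CBD use between the arms. If CBD use predicts outcome, that balance removes the between-stratum variation from the true variance of the treatment comparison. An unstratified test still counts that variation in its reference variance, so it rejects too rarely under the null and may forgo power that the allocation has already made available.

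A second loss does not depend on CBD. Fisher's exact test is discrete, and at 64 per arm its true size is well below 5%. The responder endpoints are second and third among the key secondaries, so a miss on double-blind responders also ends confirmatory testing of maintenance responders and CGI-I.

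**Working it through.** **Inputs from the documents.** 64 per arm, difference 25 points, "a common standard deviation of 43% or less", two-sided 5% (SAP 3.2, Protocol 9.4). In the 23-patient Phase 2 study "approximately half were on cannabidiol", and the responder rate was 30.4% (Protocol 1.1). **Assumed, because the documents give no figure:** the outcome gap by CBD use, the placebo responder rates, and the CGI-I distribution and odds ratios.

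**Step 1: the plan's own power.** 25 / (43 × √(2/64)) = 25 / 7.60 = 3.289, and 3.289 − 1.960 = 1.329, giving 90.8% (90.4% with the t distribution). With a Wilcoxon efficiency of 0.955, the effective n is 64 × 0.955 = 61.1 per arm and power is 89.0 to 89.5%. The stated 90% stands to within about a point.

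**Step 2: primary endpoint.** Hold the total SD at 43 and put half the participants on CBD. The within-stratum SD is √(43² − 0.25 × gap²). Under balanced strata, the unstratified statistic has a null SD of about r = (within-stratum SD)/43, so its size is about 2 × [1 − Φ(1.96/r)]. For a gap of 30: r = 40.3/43 = 0.937, 1.96/0.937 = 2.091, size 3.6%. Simulation (normal data, 100,000 replicates per cell, equal arms within stratum) agrees:

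| CBD gap (points) | Within-stratum SD | Size, formula | Size, Wilcoxon | Power, Wilcoxon | Power, van Elteren | Change |
|---|---|---|---|---|---|---|
| 0 | 43.0 | 5.0% | 5.0% | 89.0% | 88.8% | −0.2 |
| 10 | 42.7 | 4.8% | 4.8% | 89.1% | 89.1% | 0.0 |
| 20 | 41.8 | 4.4% | 4.4% | 89.5% | 90.3% | +0.8 |
| 30 | 40.3 | 3.6% | 3.6% | 90.0% | 92.1% | +2.1 |
| 43 | 37.2 | 2.4% | 2.2% | 91.5% | 95.5% | +4.0 |

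Van Elteren size was 4.9 to 5.0% throughout. With 30% on CBD the changes are −0.2, 0.0, +0.7, +1.7 and +3.2. With random stratum sizes and permuted blocks of 4 they are −0.3, +0.7, +1.9 and +4.0 at gaps of 0, 20, 30 and 43.

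If the within-stratum SD is 43 instead, Wilcoxon power falls from 88.8% at no gap to 83.3% at a gap of 43, while van Elteren stays at 88.5 to 89.3%. The total SD at that gap is √(43² + 0.25 × 43²) = 48.1, outside the planning assumption.

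**Step 3: responder endpoints.** Ganaxolone 30.4%, 64 per arm. Fisher and chi-square are by exact enumeration. CMH is by simulation with two strata of 32 per arm and no response gap by CBD (400,000 replicates).

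| Placebo rate (assumed) | Fisher | Chi-square | CMH | Fisher's loss against chi-square |
|---|---|---|---|---|
| 10% | 78.2% | 83.7% | 83.9% | 5.5 |
| 15% | 47.2% | 55.3% | 55.0% | 8.1 |
| 20% | 21.0% | 27.5% | 27.1% | 6.5 |

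With no gap the stratum contributes essentially nothing; the loss comes from Fisher. An assumed 20-point response gap by CBD use adds about 2 to 3 points over chi-square (55.3% to 58.1% at a 15% placebo rate).

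True size at common response rates of 10, 20, 30, 40 and 50%: Fisher 2.3, 3.0, 3.1, 3.5 and 3.0%; chi-square 5.1, 4.8, 5.1, 5.4 and 4.5%. Two-stratum CMH runs at 4.5 to 5.2% over the same range. A smaller run near a 20% rate with random stratum sizes (8,000 replicates, Monte Carlo standard error about 0.24 points) gave 4.85 to 5.60%.

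**Step 4: CGI-I.** Assumed treatment odds ratio 2.5 and placebo distribution 6/14/22/33/12/8/5% over the seven categories; Wald test, 20,000 replicates. At CBD odds ratios of 1, 1.5, 2 and 3, power is 82.6, 81.9, 81.4 and 79.4% with treatment only, against 82.8, 82.6, 82.9 and 82.7% with the stratum. At a CBD odds ratio of 3, the treatment-only size is 4.1%.

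**The case against.** The case for leaving the plan alone is reasonable. The tests are valid, the 90% power is not overturned, and the stratification serves its stated purpose through the planned subgroup. Nothing in the documents shows that CBD use predicts seizure change; the Phase 2 signal was somnolence. Background anti-seizure drugs must be stable before screening and the endpoint is change from each participant's own baseline, so a CBD effect on seizure level is largely absorbed already. A gain of 2 points or more on the primary needs a gap of about 30 points, larger than the 25 assumed for ganaxolone itself. Fisher guarantees size control, whereas chi-square can reach 5.4%. Adding the stratum to the CGI-I model makes its odds ratio conditional, so a median of 2.40 without the stratum against 2.54 with it partly reflects two different targets. The simulations used normal data although the SAP expects skewness, and the 30.4% comes from a small single-arm study.

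Most of this stands, and it limits the point to efficiency. It does not remove it. Stratifying costs about 0.2 to 0.3 points on the primary if CBD is irrelevant and gains more if CBD matters. The Fisher loss needs no assumption about CBD. Guaranteed size is a legitimate reason to prefer Fisher, but the SAP does not give it.

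**Conclusion.** The concern holds as two separate efficiency losses. Neither inflates type I error.

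- **Omitted stratum.** Negligible for the primary at CBD gaps up to about 10 points, under 1 point of power at 20, and 2 to 4 points at 30 to 43. It depends on CBD being prognostic, which the documents neither show nor exclude.
- **Fisher's exact test.** About 5.5 to 8 points of power on two of the four key secondaries, under the Phase 2 responder rate and placebo rates of 10 to 20%. The sequential testing makes this the more consequential part.

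The change is worth making before unblinding. Confidence is medium, because the gaps, placebo rates and odds ratios are assumptions and no skewed outcome distribution was simulated.

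**What to change.** Before unblinding, using the CBD stratum recorded at randomisation:

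1. Primary, key secondary 1 and the EMA primary: van Elteren test with a stratified Hodges-Lehmann estimate and interval. Align the population-level summary in SAP 4.3.1 with it.
2. Both responder endpoints: CBD-stratified CMH test with a stratified risk difference.
3. CGI-I: add the stratum to the proportional-odds model and state that the odds ratio is conditional on it.
4. Keep the unstratified tests, including Fisher, as sensitivity analyses.
5. Record the change in SAP section 8, since Protocol 9.3.2 also names the Wilcoxon test.

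If the sponsor keeps Fisher for guaranteed size, the SAP should give that reason and the power cost. A mid-p version would recover most of the loss (size 4.2 to 4.8% at rates of 10 to 50%) but would still ignore the stratum.

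The cost is SAP text and a little programming, with no new data. The downsides are about 0.2 to 0.3 points of primary power if CBD is not prognostic, and asymptotic rather than exact size control for the responder tests.

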4. Failure to control seizures despite appropriate trial of 2 or more ASMs at therapeutic doses and for adequate duration of treatment per PI judgment.
5. Participants should be on a stable regimen of ASMs (including moderate or strong inducer or inhibitor anti-seizure medications eg, carbamazepine, phenytoin, etc.) at therapeutic doses for ≥ 28 days prior to the screening visit, and without a foreseeable change in dosing for the duration of the study. (Note: Minor dose adjustment to address tolerability and safety events may be allowed on case-by-case basis and it should be discussed with the study medical monitor.)
6. A history of at least 8 countable seizures per month in the 2 months prior to screening with no more than 1 seizure free week in each month. This includes seizures of any kind.
7. Have at least 8 primary endpoint seizures in the first 28 days following the screening visit. The primary endpoint seizure types are defined as the following:
 - a. Focal motor seizures without impairment of consciousness or awareness.
 - b. Focal seizures with impairment of consciousness or awareness with motor features.
 - c. Focal seizures evolving to bilateral, tonic-clonic seizures.
 - d. Generalized motor seizures including tonic-clonic, bilateral tonic, bilateral clonic, or atonic/drop seizures.

Seizures that **do not count** towards the primary endpoint include:

- a. Focal or generalized nonmotor seizures (eg, absence seizures or focal nonmotor seizures with or without impairment of awareness).
- b. Infantile or epileptic spasms.
- c. Myoclonic seizures.
8. Participants with surgically implanted vagal nerve stimulator (VNS) will be allowed to enter the study provided that all of the following conditions are met:
 - a. The VNS has been in place for ≥ 6 months prior to the screening visit.
 - b. The settings must have remained constant for 3 months prior to the screening visit and are expected to remain constant throughout the study.
 - c. The battery is expected to last for the duration of the study.
9. Parent(s)/caregiver(s)/LAR(s) or the participant, as appropriate, is (are) willing and able to maintain an accurate and complete daily seizure eDiary for the duration of the study.
10. Willing and able to take IP (suspension) as directed with food (tid).

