9.4 Sample Size Determination

Approximately 200 participants with TSC will be screened with the aim of randomizing approximately 128 participants into 2 treatment groups in a 1:1 ratio.

Testing of treatment effect (the actual analysis will use a Wilcoxon rank-sum test, which has approximately the same power as the Analysis of Variance [ANOVA]) for GNX vs placebo will be performed using a 5% 2-sided alpha level. A total of 64 participants per group provides at least 90% power for the primary endpoint assuming an estimate of the treatment effect difference that is at least 25% and a common standard deviation of 43% or less.

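### The primary Wilcoxon test is valid but ignores baseline seizure frequency; a pre-specified rank ANCOVA would add about 0 to 4 points of power with no more participants

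*SAP*

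**What the plan says.** SAP 4.3.2 states that "the test will be performed using the Wilcoxon Rank-Sum statistic using a 2-sided significance level of 0.05", and gives a Hodges-Lehmann median difference with a 95% interval. Protocol 9.3.2 specifies the same test. SAP 4.3.4 repeats it for key secondary 1 (percent change over the maintenance period), and SAP section 7 bases the EMA primary analysis on the maintenance period. No covariate or stratum enters any of these tests, and none of the sensitivity analyses listed in protocol 9.3.2.1 or SAP 4.3.3 adds one.

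Baseline is available for everyone. It enters the endpoint as the denominator: "Baseline 28-day seizure frequency will be calculated as the total number of seizures in the baseline phase", scaled to 28 days over the days with diary data. It is also an entry requirement: "Have at least 8 primary endpoint seizures in the first 28 days following the screening visit" (protocol 5.1, criterion 7). Randomization is stratified only on CBD (Epidiolex) use.

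On power, SAP 3.2 says "Sixty-four subjects per group provides at least 90% power for the primary endpoint", for a "difference that is at least 25% and a common standard deviation of 43% or less". It treats the rank-sum test as one "which has approximately the same power as the ANOVA".

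**The concern.** Dividing by baseline is not the same as adjusting for it. A 28-day seizure count is a noisy measure of a participant's usual rate. A baseline that is high by chance inflates the denominator and tends to be followed by a larger percent fall. A low one does the reverse. Percent change is therefore likely to be negatively related to baseline.

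Two things follow. Variation that baseline could explain stays in the error term, which costs some power. And if the arms happen to differ in baseline frequency, the unadjusted comparison shifts with that difference. Stratifying on CBD use does not control baseline frequency, and the plan has no pre-specified adjusted analysis to set against such an imbalance.

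**Working it through.** **Inputs.** From SAP 3.2: n = 64 per arm, difference 25 points, SD 43 points. Two-sided alpha is 0.05 (SAP 4.3.2; protocol 9.4). The correlation r between baseline frequency and percent change is not in the documents and is varied from 0 to 0.4.

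**1. The plan's own figure.** Power = Φ(δ / (σ√(2/n)) − 1.96).
- σ√(2/n) = 43 × 0.1768 = 7.601, and 25 / 7.601 = 3.289.
- Φ(3.289 − 1.96) = Φ(1.329) = 90.8%. The noncentral t gives 90.4%, and 63 per arm suffice for 90% under the normal formula. The stated 90% reproduces.

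**2. The planned test.** Under normality the Wilcoxon test has efficiency 3/π relative to the t-test.
- √(3/π) = 0.977, and 3.289 × 0.977 = 3.214.
- Φ(3.214 − 1.96) = Φ(1.254) = 89.5%. Simulation gives about 89%.

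**3. Effect of adjustment.** The residual SD is 43√(1 − r²), so approximate rank-test power is Φ(3.214 / √(1 − r²) − 1.96). The last three columns are from 40,000 simulated normal-model trials per setting.

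| \|r\| | Residual SD | Formula power (gain) | Wilcoxon | Rank ANCOVA | Difference |
|---|---|---|---|---|---|
| 0 | 43.0 | 89.5% (0) | 88.9% | 88.6% | −0.3 |
| 0.1 | 42.8 | 89.8% (+0.3) | 89.0% | 89.2% | +0.2 |
| 0.2 | 42.1 | 90.7% (+1.2) | 89.3% | 90.3% | +1.0 |
| 0.3 | 41.0 | 92.1% (+2.6) | 89.0% | 91.1% | +2.1 |
| 0.4 | 39.4 | 93.9% (+4.4) | 88.9% | 93.0% | +4.1 |

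Simulated type I error was 4.8 to 5.0% for both tests.

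**4. What r might be.** Two count models were tried, both with assumed parameters and both applying the entry rule of at least 8 seizures.
- Overdispersed counts with median 45 per 28 days, between-participant log SD 0.8 to 1.1 and window-to-window log SD 0.2 to 0.5 gave r from −0.07 to −0.38. Over 12 scenarios with Wilcoxon power near 89%, rank ANCOVA gained 0.1 to 4.2 points, typically 1 to 2. Type I error was 4.7 to 5.4%.
- A negative binomial model with median 20 to 60 gave rank correlations from about −0.05 to −0.32.

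**5. What drives r.** In a log-normal/Poisson version, the entry rule removed only 2 to 8% of participants. It weakened the rank correlation each time: −0.27 to −0.24, −0.48 to −0.44, −0.21 to −0.15 and −0.37 to −0.31. Noise in the denominator produces the correlation; the entry rule does not. One of these settings stays a little above 0.4 in size. At |r| = 0.5 the simulated gain was 6.2 points, so 0.4 is a working limit and not a proven ceiling.

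**6. Chance imbalance.** The standard error of the between-arm difference in standardized baseline is √(2/64) = 0.177. A difference beyond 0.25 SD is 0.25 / 0.177 = 1.41 standard errors, which occurs in about 16% of trials (8% in each direction).
- When it went against GNX, Wilcoxon power fell to 82% at |r| = 0.2 and 76% at 0.3. Rank ANCOVA held about 90% in both.
- With no true effect and |r| = 0.3, the Wilcoxon test rejected in about 7 to 8% of the imbalanced trials, against 4 to 5% for rank ANCOVA.

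**The case against.** The strongest reply is that the planned analysis is sound and coherent. The Wilcoxon test and the Hodges-Lehmann interval form a matched pair, and the test is chosen because skewness and outliers are expected. The endpoint is already scaled to each participant's own baseline. Regression to the mean acts on both arms alike under 1:1 randomization. All of this stands.

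It also stands that the size of the gain rests on a correlation the documents do not supply, and that at |r| near 0 there is no gain and a loss of up to about 0.3 points. Nor is the change without cost. The adjusted p-value would open the gate to the four key secondaries while the interval still came from the unadjusted procedure. In simulation the two tests disagreed in about 3% of trials at |r| = 0.2 and 4 to 5% at 0.3. In about 1% the adjusted test lost a result that Wilcoxon had won. The proposed model also omits the stratification factor; whether to include it is a separate choice that was not evaluated here.

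What the reply does not answer is the conditional problem. If a baseline imbalance arises, the plan has no pre-specified analysis that accounts for it.

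**Conclusion.** The point holds as an efficiency and robustness improvement. For |r| from 0 to 0.4, rank ANCOVA changes power by about 0 to +4 points, typically 1 to 2, from about 89%. It needs no extra participants or data and keeps type I error at 5%. The figures assume the SAP's 25-point difference and SD of 43, full data on 64 per arm (no dropout allowance is stated) and an assumed correlation.

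A reader might infer three stronger things that the documents do not support.
- That the trial misses its power target. The gap between 89% and 90% falls within the SAP's claim of approximately equal power to ANOVA, and the difference and SD are stated as bounds.
- That the unadjusted test is biased or inflates type I error. Averaged over randomizations it does not. The inflation in step 6 applies only to trials with an imbalance.
- That selecting on at least 8 baseline seizures creates the problem. In the count model that rule slightly weakened the correlation.

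**What to change.** Before unblinding, specify rank ANCOVA in SAP 4.3.2, in SAP 4.3.4 for key secondary 1, and in SAP section 7 for the EMA primary. The model is ranked percent change on treatment, with ranked baseline 28-day seizure frequency as covariate. Keep the Hodges-Lehmann estimate and interval, and state that they are unadjusted. Report the unadjusted Wilcoxon test as a sensitivity analysis in SAP 4.3.3. Record the departure from protocol 9.3.2 in SAP section 8, which at present lists only the changed ITT definition.

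The cost is SAP text and one model per endpoint, plus the possible disagreement between p-value and interval described above. If the sponsor prefers to keep the matched pair as primary, adding rank ANCOVA as a pre-specified sensitivity analysis would still provide an answer to a baseline imbalance, though not the power gain. SAP 4.3.3 announces five sensitivity analyses and numbers four, so that section needs an edit in any case.
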